8.2.5. Electronic Columbia-Suicide Severity Rating Scale

No signal of suicidal ideation and behavior has been observed in the clinical trials of guselkumab to date. However, in light of reports concerning suicidal ideation and behavior in patients with plaque psoriasis treated with an IL-17R antagonist (brodalumab),⁶ the eC-SSRS will be used as a screening tool to prospectively evaluate suicidal ideation and behavior among study participants. The eC-SSRS measures 5 possible levels of suicidal ideation and 4 possible suicidal behaviors, as well as non-suicidal self-injurious behavior. The assessment is a fully-structured, subject self-report eC-SSRS questionnaire, including standardized questions, follow-up prompts, error handling routines, and scoring conventions.^{24,29} Two versions of the eC-SSRS will be used in this study, the *Lifetime* version and the *Since Last Contact* version. The *Lifetime* version will be conducted during the screening visit and the *Since Last Contact* version will be conducted at all other visits.

Participants will complete the eC-SSRS questionnaire using the sponsor-provided electronic device. Study site personnel will train the participants on how to use the electronic device. The eC-SSRS will be provided in the local languages in accordance with local guidelines.

The eC-SSRS will be performed during each evaluation visit according to the SoA. During a visit, participants will be directed to a private, quiet place with the electronic device to complete the assessment. Participants who do not have suicidal behavior or ideation will answer a limited

number of questions and will usually complete the assessment in about 3 minutes. Participants with significant suicidal ideation and behavior may require up to 10 minutes to answer all relevant questions. At the screening visit, the eC-SSRS should be completed as the first assessment after signing informed consent and before any other tests, procedures, or other consultations. For subsequent visits, the eC-SSRS should be completed after all PROs and before any other tests, procedures, or other consultations.

At the conclusion of each assessment, the eC-SSRS Findings Report can be viewed electronically. At screening (“In the last 6 months”) and Week 0, participants with an Ideation level (1-5) or any suicidal behaviors or with a response of “YES” for non-suicidal, self-injurious behavior must be determined to be not at risk by the investigator based on an evaluation by a mental health professional in order to be randomized. Participants with an Ideation level (1-5) on the eC-SSRS or any suicidal behaviors or with a response of “YES” for non-suicidal, self-injurious behavior at any postbaseline visit will also be referred to an appropriate mental health professional for evaluation. If a participant’s psychiatric disorder can be adequately treated with psychotherapy and/or pharmacotherapy then the participant, at the discretion of the investigator, should be continued with treatment. Ultimately, the determination of suicidality and risk is up to the investigator’s clinical judgment following evaluation by a mental health professional (eg, psychiatrist, psychologist, or appropriately trained social worker or nurse).

Positive reports are generated from the eC-SSRS vendor for ANY of the following findings:

- Ideation level 4: Some intent to act, no plan
- Ideation level 5: Specific plan and intent
- Behaviors: Actual suicide attempts
- Behaviors: Interrupted attempts
- Behaviors: Aborted attempts
- Behaviors: Preparatory actions.

Negative suicidality indication reports are generated from the eC-SSRS vendor when there are NO indications of the above.

The participant should not leave the site at screening or be dosed at dosing visits before the eC-SSRS Findings Report (both for negative and positive reports) is reviewed by the investigator and the participant’s risk has been assessed and follow-up determined, as appropriate.

For each Ideation level and Behavior, the following actions and associated alerts will be generated, if applicable:

- No ideation with No Behaviors: No further action is needed.
- Ideation Levels (1-5) or suicidal behavior: Participant risk assessed and referral to a mental health professional.

Ideation level of a 1, 2, or 3 with No Behaviors: Negative findings report will be generated.

Ideation level of a 4 or 5 or any suicidal behavior: Positive findings report will be generated. When the system reports that the participant has a positive suicidal indication (including for an incomplete-positive assessment), the site can immediately see the outcome via the electronic device.

- Non-suicidal, self-injurious behavior YES: Participant risk assessed and referral to a mental health professional. Negative findings report will be generated.

Interruption or the discontinuation of study treatment should be considered for any participant who reports suicidal Ideation level 4 (some intent to act, no plan), Ideation level 5 (specific plan and intent), or any suicidal behavior (actual suicide attempts, interrupted attempts, aborted attempts, or preparatory actions) on a postbaseline (after Week 0) eC-SSRS assessment and who is deemed to be at risk by the investigator based upon evaluation by a mental health professional. Discussion of such participants with the medical monitor or designee is required (see Section 7.1). The final decision on suitability for continuing in the study will be made by the investigator.

Any eC-SSRS findings, which in the opinion of the investigator are new or considered to be a worsening and clinically significant, should be reported on the AE eCRF (see Appendix 10 [Section 10.10], Adverse Events, Serious Adverse Events, Product Quality Complaints, and Other Safety Reporting: Definitions and Procedures for Recording, Evaluating, Follow-up, and Reporting).

8.2.6. Concomitant Medication Review

Concomitant medications will be reviewed at each visit.

8.2.7. Injection-Site Reactions

An injection-site reaction is any adverse reaction at a SC study intervention injection-site. Injection sites will be evaluated for reactions and any injection-site reaction will be recorded as an AE.

8.2.8. Hypersensitivity Reactions

Before any administration of study intervention at the study site, appropriately trained personnel and medications (eg, antihistamines, injectable epinephrine) must be available to treat hypersensitivity reactions, including anaphylaxis. All participants must be observed carefully for signs and symptoms of a hypersensitivity reaction (eg, urticaria, pruritis, angioedema, wheezing, dyspnea, or hypotension).

8.2.9. Adverse Events Temporally Associated with Infusion

Any AE (except laboratory abnormalities) that occurs during or within 1 hour after the IV infusion of study intervention will be carefully evaluated. Minor infusion-related AEs may be managed by slowing the rate of the IV infusion and/or treating with antihistamines and/or acetaminophen (paracetamol) as clinically indicated. If an IV infusion of study intervention is interrupted because of an AE that, in the opinion of the investigator, is not severe or does not result in an SAE, the infusion may be restarted with caution.

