	
Infections have been identified as adverse reactions of guselkumab, including respiratory infections, herpes simplex and tinea infections, and gastroenteritis.
	
HCV), will be excluded from the study. Similarly, participants with evidence of active or untreated latent tuberculosis (TB) will be excluded from the study (Section 5.1.1).
 
 • Participants who have received a live viral or bacterial vaccination within 12 weeks of baseline will be excluded from the study. In addition, participants must agree not to receive a live viral or live bacterial vaccination during the study and for 12 weeks after receiving the last dose of study intervention (Section 5.1.1). • Participants will be instructed to seek medical attention if they develop signs or symptoms suggestive of an infection, and investigators are instructed in the protocol to monitor for signs or symptoms of infections, including TB (Sections 8.2.10 and 8.2.11). • Discontinuation of a participant’s study intervention must be strongly considered if the participant develops a serious infection, including but not limited to sepsis or pneumonia. In addition, any serious infection should be discussed with the medical monitor or designee, and study intervention should be withheld until the clinical assessment is complete (Section 7.1).

Hypersensitivity reactions, including serious hypersensitivity reactions.
	
Serious hypersensitivity reactions including anaphylaxis have been reported in postmarketing experience with guselkumab in psoriasis patients.
 
Hypersensitivity, including anaphylaxis, urticaria and rash have been identified as adverse drug reactions for guselkumab.
	
 • Participants with known allergy, hypersensitivity, or intolerance to guselkumab or its excipients will be excluded from the study. • Sites are instructed that before any administration of study intervention, appropriately trained personnel and medications (eg, injectable epinephrine) must be available to treat hypersensitivity reactions, including anaphylaxis. In addition, all participants must be observed carefully for signs and symptoms of a hypersensitivity reaction (eg, urticaria, pruritis, angioedema, wheezing, dyspnea, or hypotension) (Section 8.2.8). • Any participant who develops a serious hypersensitivity reaction such as anaphylaxis must discontinue study intervention (Section 7.1).

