A participant receiving treatment for latent TB discontinues this treatment prematurely or is noncompliant with the therapy.

- The participant has a serious adverse reaction that is related to an injection or an infusion resulting in bronchospasm with wheezing and/or dyspnea that requires ventilatory support OR that results in symptomatic hypotension with a decrease in systolic blood pressure >40 mm Hg or blood pressure <90/60 mm Hg.
- The participant has a reaction resulting in myalgia and/or arthralgia with fever and/or rash (suggestive of serum sickness and not representative of signs and symptoms of other recognized clinical syndromes) occurring 1 to 14 days after an injection of study intervention. These may be accompanied by other events including pruritus, facial, hand, or lip edema, dysphagia, urticaria, sore throat, and/or headache.
- The participant has a malignancy including squamous cell skin cancer. Consideration may be given to allowing participants who develop ≤ 2 basal cell skin cancers that are adequately treated with no evidence of residual disease to continue to receive study intervention.
- Participant requires dialysis.
- Noncompliance with study drug administration defined as multiple episodes of missing the window in which to receive study intervention.
- The participant has severe liver test abnormalities that meet one of the conditions outlined in Appendix 11 (Section 10.11; Liver Safety: Suggested Actions and Follow-up Assessments).

The sponsor may elect to terminate the study at any time, and if the sponsor decides not to continue development for any reason, study medication/drug will no longer be provided to any participants, including those in the LTE.

Discontinuation of a participant's study intervention should be considered under the following conditions:

1. Persistent inadequate response or worsening of LN based on worsening of renal function.
2. If the participant initiates treatment with prohibited therapies for SLE or LN, the medical monitor or designee should be notified for possible discontinuation of study intervention (Section 6.5).
3. The participant develops a serious infection, including but not limited to sepsis or pneumonia.
Note: Any serious infection should be discussed with the medical monitor or designee, and study intervention should be withheld until the clinical assessment is complete.

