4. Discontinuation of study treatment should be considered for participants who report suicidal Ideation level 4 (some intent to act, no plan), Ideation level 5 (specific plan and intent), or any suicidal behavior (actual suicide attempts, interrupted attempts, aborted attempts, or preparatory actions) on a postbaseline (after Week 0) eC-SSRS assessment. Discussion of such subjects with the medical monitor or designee is required.
5. The participant develops a severe injection-site or infusion reaction, but not meeting criteria specified above.

If a participant discontinues study intervention for any reason before the end of the double-blind phase they may continue in the study. If the participant wishes to discontinue the study, then the Final Efficacy Visit and final safety visit assessments should be obtained as specified in the SoA

(Section 1.3, or as noted in Footnote c of the SoA). Study intervention assigned to the participant who discontinued study intervention may not be assigned to another participant.

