10.10.3. Severity Criteria

An assessment of severity grade will be made using the following general categorical descriptors:

Mild: Awareness of symptoms that are easily tolerated, causing minimal discomfort and not interfering with everyday activities.

Moderate: Sufficient discomfort is present to cause interference with normal activity.

Severe: Extreme distress, causing significant impairment of functioning or incapacitation. Prevents normal everyday activities.

The investigator should use clinical judgment in assessing the severity of events not directly experienced by the participant (eg, laboratory abnormalities).

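### Section 8.2.9 bars restarting an interrupted infusion only when the reaction is both severe and serious, and this is not reconciled with the mandatory stops in Sections 7.1 and 2.3.1

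*Protocol*

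**What the plan says.** Protocol Section 8.2.9 deals with adverse events during an infusion or within an hour after it. When an infusion has been interrupted for an event that, in the investigator's opinion, "is not severe or does not result in an SAE, the infusion may be restarted with caution". The section does not refer to Section 7.1.

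Section 7.1 has two tiers.

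- **Mandatory stop.** One item reads "The participant has a serious adverse reaction that is related to an injection or an infusion resulting in bronchospasm with wheezing and/or dyspnea", qualified by a need for ventilatory support. Its alternative limb is a reaction that "results in symptomatic hypotension with a decrease in systolic blood pressure >40 mm Hg or blood pressure <90/60 mm Hg". The item requires the reaction to be serious. It does not mention a severity grade.
- **Stop to be considered.** The second list is introduced by the words "study intervention should be considered under the following conditions". Its fifth item is "The participant develops a severe injection-site or infusion reaction, but not meeting criteria specified above".

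The risk table in Section 2.3.1 adds a further mandatory rule: "Any participant who develops a serious hypersensitivity reaction such as anaphylaxis must discontinue study intervention". It cites Section 7.1 as the source, but no item in Section 7.1 is worded in terms of serious hypersensitivity or anaphylaxis.

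Appendix 10 keeps the two features apart. Section 10.10.3 defines severe by intensity ("Extreme distress, causing significant impairment of functioning or incapacitation"). Section 10.10.1 defines serious by outcome or medical importance, for example an inpatient admission.

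**The concern.** Section 8.2.9 is the passage a site would turn to while an infusion is on hold. Read as written, it gives permission if either condition is met, so a reaction that is only severe, or only serious, does not block a restart. Some serious reactions are mandatory stops elsewhere in the protocol whatever their grade, and nothing in Section 8.2.9 sends the reader there. By contrast, the next section on infections, 8.2.10, does point to Section 7.1. It may also be unknown when the decision is made whether an event will turn out to be serious, so the second condition can look satisfied too early.

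What is at stake is re-exposure of a participant whom another section requires to be taken off study intervention. This would happen in the IV phase, where Table 4 predicts the higher exposure (mean Cmax 109 µg/mL, against 30 µg/mL for SC maintenance). Every participant is scheduled for three infusions, at Weeks 0, 4 and 8.

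**Working it through.** The plan gives no figure to reproduce. The check is a truth table for the restart condition, set beside the other sections.

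**Inputs.** Restart condition: Section 8.2.9. Mandatory and discretionary stops: Section 7.1. Serious hypersensitivity: Section 2.3.1. Definitions of severe and serious: Sections 10.10.3 and 10.10.1.

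**Literal condition.** Restart allowed = (not severe) OR (not serious). By elementary logic this equals NOT (severe AND serious).

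| Reaction | 8.2.9 as written | 7.1 and 2.3.1 | Result |
|---|---|---|---|
| Not severe, not serious | Restart allowed | No specific infusion-reaction rule | Consistent |
| Severe, not serious | Restart allowed | 7.1, second list, item 5: consider stopping | Tension, not contradiction |
| Serious, not severe | Restart allowed | 7.1: must stop if the bronchospasm or hypotension features are met; 2.3.1: must stop for serious hypersensitivity; otherwise no specific rule | Direct conflict where one of the mandatory rules is met |
| Severe and serious | Restart not allowed | Must stop if the mandatory rules are met; otherwise consider stopping | No conflict with a mandatory stop |

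The literal wording allows a restart in 3 of the 4 combinations. If it were read as neither severe nor serious, it would allow a restart in 1 of 4, and the third row would no longer conflict.

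**Can the third row occur?** Yes. A reaction graded moderate that leads to admission is serious without being severe. The limbs differ in how readily this happens:

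- *Bronchospasm limb.* A reaction needing ventilatory support would rarely be graded below severe, given how Section 10.10.3 defines that grade. If it is graded severe it falls in the fourth row, where Section 8.2.9 does not allow a restart.
- *Hypotension limb.* A serious reaction with symptoms and blood pressure beyond the stated limits can plausibly be graded below severe. It then passes the restart test but is a mandatory stop under Section 7.1.
- *Serious hypersensitivity.* The same applies through Section 2.3.1, with the added difficulty that the Section 7.1 item it relies on is not there in those words.

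**Do the sections govern the same act?** Section 8.2.9 concerns resuming one infusion, and Section 7.1 concerns ending study intervention. Giving the rest of an interrupted infusion is still giving study intervention, so the two acts overlap once a stop is mandatory. They need not overlap where Section 7.1 only asks for consideration.

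**The case against.** The strongest reply has four parts.

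1. **The permission is discretionary.** Section 8.2.9 says the infusion may be restarted, leaves the judgement to the investigator and does not claim to override Section 7.1. Section 7.1 also has a general mandatory item for cases where the investigator thinks stopping is best for the participant on safety or tolerability grounds. A careful reader can obey both sections. This stands as far as it goes: the mandatory rules still bind. But compliance then depends on the reader knowing to look in Section 7.1, and Section 8.2.9 does not say so.
2. **The phrase may be meant as neither severe nor serious.** The preceding sentence is about minor reactions, which favours that reading. It is plausible and would remove the conflict, but it is not what the sentence says. A safety instruction should not need its conjunction corrected by the site.
3. **A reader might infer that Section 8.2.9 contradicts Section 7.1 for every severe or every serious reaction.** The documents do not support that. For a severe, non-serious reaction, an instruction to consider stopping is compatible with a permission to restart cautiously. For serious reactions, the Section 7.1 infusion-reaction item is limited to the bronchospasm and hypotension features.
4. **A reader might also infer a measurable effect on the primary endpoint.** Stopping study intervention, other than for COVID-19 reasons, counts as non-response in the primary composite estimand (SAP Section 5.3.2.1). That rule applies however Section 8.2.9 is worded, and Section 7.1 already leaves some stops to judgement. No frequency or direction of effect can be derived from the documents, so no claim of bias is made here.

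**Conclusion.** Wrong as written, on a narrow front. Section 8.2.9, followed literally, permits a restart that Section 7.1 or Section 2.3.1 prohibits. The direct conflict is confined to serious reactions graded below severe that meet the hypotension features or are serious hypersensitivity reactions; the bronchospasm features qualify formally but would seldom be graded that low. For severe, non-serious reactions there is only an unaddressed tension with the discretionary item in Section 7.1.

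The 3-of-4 against 1-of-4 count describes the logic of the sentence. It is not a rate: the four combinations are not equally likely and the documents give no incidence for any of them. Screening of new participants has stopped, so any remaining infusions are limited to people already screened or randomized.

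The conclusion assumes that *or* is read literally and that severity is graded under Section 10.10.3 independently of seriousness. It takes no view on which clinical rule is right.

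**What to change.** Reconcile Sections 8.2.9, 7.1 and 2.3.1:

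- In Section 8.2.9, state whether severity alone, seriousness alone, or only the two together bars a restart.
- Add a cross-reference from Section 8.2.9 to Section 7.1, and say how the restart permission stands in relation to the mandatory stops and the discretionary item there. The two-tier structure of Section 7.1 need not change.
- Align Section 2.3.1 with Section 7.1, so that the serious-hypersensitivity rule it attributes to Section 7.1 can be found there or is cited correctly.

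The content of the clinical rule is the sponsor's decision.

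The cost is about one sentence and a cross-reference in Section 8.2.9, plus a small alignment of Sections 2.3.1 and 7.1. Sample size, endpoints and analysis are unaffected. Under Section 10.9.1, a protocol clarification communication would do if the sponsor judges that study conduct does not change. If conduct does change, an amendment is needed.

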8.2.10. Infections

Investigators are required to evaluate participants for any signs or symptoms of infection at scheduled visits. Study intervention administration should not be given to a participant with a clinically significant, active infection. If a participant develops a serious infection, including but not limited to sepsis or pneumonia, discontinuation of study intervention must be strongly considered (Section 7.1). Any serious infection should be discussed with the medical monitor or designee, and study intervention should be withheld until the clinical assessment is complete.

8.2.11. Tuberculosis Evaluations

8.2.11.1. Initial Tuberculosis Evaluation

Participants must undergo testing for TB (refer to Appendix 3 [Section 10.3]) and their medical history assessment must include specific questions about a history of TB or known occupational or other personal exposure to individuals with active TB. The participant should be asked about past testing for TB, including chest radiograph results and responses to tuberculin skin or other TB testing. Investigators have the option to use both the QuantiFERON-TB[®] test and the tuberculin skin test to screen for latent TB if they believe, based on their judgment, that the use of both tests is clinically indicated to evaluate a participant who is high risk of having latent TB. If either the QuantiFERON-TB[®] test or the tuberculin skin test is positive, the participant is considered to have latent TB infection for the purposes of eligibility for this study.

Participants with a negative QuantiFERON-TB[®] test result (and a negative tuberculin skin test result in countries in which the QuantiFERON-TB[®] test is not approved/registered or the tuberculin skin is mandated by local health authorities) are eligible to continue with pre-randomization procedures. Participants with a newly identified positive QuantiFERON-TB[®] test result must undergo an evaluation to rule out active TB and initiate appropriate treatment for latent TB. Appropriate treatment for latent TB is defined according to local country guidelines for immunocompromised patients. If no local country guidelines for immunocompromised patients exist, US guidelines should be followed, or the participant will be excluded from the study.

A participant whose first QuantiFERON-TB[®] test result is indeterminate should have the test repeated. In the event that the second QuantiFERON-TB[®] test result is also indeterminate, the participant may be enrolled without treatment for latent TB if active TB is ruled out, their chest radiograph shows no abnormality suggestive of TB (active or old, inactive TB) and the participant has no additional risk factors for TB as determined by the investigator. This determination must be promptly reported to the medical monitor or designee and recorded in the participant's source documents and initialed by the investigator.

